**Table 6: Calculation of Imputed ADCS-ADL Instrumental Score (Study RVT-101-2001)**

Missing Question	Imputed Instrumental formula
8a, 8b, 8c, 16b, 18a,18b, 18c,19a,19b,19c, 20a, 20b	Observed total*(1+1/55)
9, 10, 11, 12, 14, 16a, 17, 21, 22b	Observed total*(1+3/53)
13, 15, 23b	Observed total*(1+4/52)
7	Observed total*(1+5/51)

The total ADCS-ADL score will be calculated by adding up the Basic total score and the Instrumental imputed total score.

The Total Independence score will give any missing score from either Basic or Instrumental questions a value of zero.

In cases where 2 or more questions are missing, the total Instrumental score will not be imputed.

The Independence score will assign a '0' to any question that is missing.

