### **5.4. Alzheimer's Disease Cooperative Study - Activities of Daily Living (ADCS-ADL)**

The ADCS-ADL (Alzheimer's Disease Cooperative Society - Activities of Daily Living) scale [[Galasko 1997](#)] measures functional impairment in terms of activities of daily living. The ADCS-ADL is an interviewer-administered informant-based scale where the informant (caregiver) responds to 23 activities of daily living questions about the subject. There are 4 scores derived: the Total score, Basic score, Instrumental score, and the Independence Score.

The questions range from basic to instrumental activities of daily living and take approximately 20 minutes to complete. The Total score ranges from 0-78 and a higher score signifies greater functional ability; the lower the score the greater (worse) the impairment.

The questionnaire is split into two types of questions, an initial question relating to whether a subject has completed a particular activity and then a follow-on question which scores how much assistance the subject has required if they have performed that particular activity.

- The Total score is calculated by adding up the responses for each of the individual activities. Note if a caregiver responds to the question relating to whether the subject performed a particular activity as no or don't know this will contribute a zero to the Total score.
- The Basic score will also be calculated as the sum of questions 1-6b and ranges from 0-22 (activities included in the basic score are: eating, walking, using the toilet, bathing, grooming and dressing)
- The Instrumental score is the sum of questions 7-23 and ranges from 0-56 (the Instrumental score includes: using the telephone, watching television, conversations, clearing dishes, personal belongings, making drinks, making snacks, taking rubbish out, getting out and about, shopping, keeping appointments, being left alone, current events, reading, writing, pastimes/hobbies, household chores).
- The Independence Score is calculated by re-scoring all 23 individual questions for each activity, such that a given question is given a '1' if the MAXIMUM (best) score is observed, and a '0' otherwise. Thus, each question contributes a maximum of 1 unit to the total, with a total range for the Independence Score ranging from 0 (worst) to 23 (best).

If there are any missing scores within the Basic activities questions, the Basic total score will be not be imputed and therefore will be set to missing.

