If there is only one missing score within the Instrumental activities questions, the Instrumental score will be calculated as a weighted average of the scores provided for the remaining 16 activities as follows (and see [Table 6](#)):

- $\text{Imputed Total} = \text{Observed Total Score} \times \frac{(1 + \text{Maximum Score of the missing value})}{\text{Sum of the Maximum Score of the non -missing values}}$

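### SAP 5.4 scores every unanswered ADCS-ADL question as not independent on the Independence score, with no limit on missing items, so gaps can create false change in either direction on this tertiary subscore

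*SAP*

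**What the plan says.** SAP 5.4 derives four scores from one interview: Total, Basic, Instrumental and Independence. For Independence, "a given question is given a '1' if the MAXIMUM (best) score is observed, and a '0' otherwise", so the score counts activities at their best level and a higher count is better.

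The missing-item rules differ by score:

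- **Basic:** with any item missing, "the Basic total score will be not be imputed and therefore will be set to missing".
- **Instrumental:** "If there is only one missing score within the Instrumental activities questions, the Instrumental score will be calculated as a weighted average", using Table 6. Beyond that, "In cases where 2 or more questions are missing, the total Instrumental score will not be imputed".
- **Total:** Basic plus the (possibly imputed) Instrumental score, so it cannot be formed without both.
- **Independence:** "The Total Independence score will give any missing score from either Basic or Instrumental questions a value of zero", and again, "The Independence score will assign a '0' to any question that is missing". No maximum number of gaps is given, and no condition makes the score missing.

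SAP 9.4.2 lists change from Baseline in the Independence subscore among the tertiary analyses, by MMRM and Wilcoxon test on observed data. No sensitivity analysis for missing items is specified for it.

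**The concern.** Under this rule, a question nobody answered takes the same value as a question answered below its best level. The result then enters the MMRM and the Wilcoxon test as though it had been observed. A form judged too incomplete to give a Basic or Total score still gives an Independence score, pulled downward by its gaps. A change score built from one complete form and one incomplete form contains change that did not happen.

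The rule also stands apart from most scoring rules in the same SAP. ADAS-Cog (5.2) gives the worst score only when the item was not completed for cognitive reasons. UPDRS-III (5.1) uses the mean of the answered items, with a cut-off. COWAT (5.5), NPI (5.6) and the Dependence Scale (5.9) go to missing. NEVHI (5.7.1) does score a missing frequency as 0, but only once a Phenomenology total exists.

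At stake is the credibility of one tertiary subscore, and of its treatment difference if gaps are more common in one arm.

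**Working it through.** **1. The plan's own figures reproduce.** Independence maximum: 6 Basic + 17 Instrumental activities = 23. Instrumental maximum from Table 6: 12×1 + 9×3 + 3×4 + 1×5 = 56. The Table 6 denominators are 56 − 1 = 55, 56 − 3 = 53, 56 − 4 = 52 and 56 − 5 = 51. Total: 22 + 56 = 78. All agree with SAP 5.4.

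**2. The same gap under each rule.**

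| Unanswered | Basic | Instrumental | Total | Independence |
|---|---|---|---|---|
| 1 Basic item | missing | unaffected | missing | calculated, gap = 0 |
| 1 Instrumental item | unaffected | prorated | calculated | calculated, gap = 0 |
| 2 or more Instrumental items | unaffected | not imputed | none (natural reading) | calculated, gaps = 0 |

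**3. Effect on one stable subject.** Let I be the number of the 23 activities truly at maximum and k the number unanswered at one visit. If the gaps fall at random over activities, the expected false shift in that visit's score is −k×I/23, and the worst case is −min(k, I). The documents give neither a typical I nor an item-missing rate, so both are assumptions. With I = 16:

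| k | Expected shift | Worst case |
|---|---|---|
| 1 | −0.70 | −1 |
| 2 | −1.39 | −2 |
| 3 | −2.09 | −3 |
| 5 | −3.48 | −5 |

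For k = 3, the expected shift runs from −1.04 (I = 8) to −3.00 (I = 23).

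The sign of the false *change* depends on the visit. For k = 3 and I = 16 it is −2.09 if the gap is at Week 24 only, +2.09 if at Baseline only, and 0 if the same activities are missing at both.

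A concrete case: a subject scores 16 at Baseline, and three Basic activities that had been at maximum are unanswered at Week 24. Basic and Total are missing. Independence is 13, a change of −3 (3/23 = 13% of the scale) with no real change.

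**4. Effect on group means.** If a fraction f of Week 24 forms lack k activities, the mean shifts by −f×k×I/23. With I = 16:

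- f = 10%, k = 1: 0.10×1×16/23 = 0.07 points lost.
- f = 20%, k = 3: 0.20×3×16/23 = 0.42 points lost.
- f = 15% in one arm and 5% in another, k = 3: (0.15 − 0.05)×3×16/23 = 0.21 points of spurious difference, or 0.21/23 = 0.9% of the scale.

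With equal f in both arms, the difference is unbiased to first order.

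**5. How often the scores part company.** Treat each activity as one question with an independent 1% chance of being unanswered. Basic is lost in 1 − 0.99^6 = 5.9% of forms. Instrumental is lost in 1 − 0.99^17 − 17×0.01×0.99^16 = 1.2%. Total is lost in 1 − (1 − 0.059)(1 − 0.012) = 7.0%. At 2%, Total is lost in 15.4%. Every one of these forms would still carry an Independence value.

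**The case against.** The best defence is that this is a stated choice. The item definition gives 1 only when the best score is observed, so an unanswered item falls under the 0 branch, and the SAP says so twice. A binary count need not share the missing-item rule of a graded sum, and scoring 0 for independence not shown may be thought conservative. It is true that the text does not contradict itself. The rule is not conservative, however: a Baseline gap produces apparent improvement, and in the treatment comparison it favours whichever arm has the more complete Week 24 forms.

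A second defence is that a response of don't know already scores 0 in the Total. That covers a question that was answered. The SAP treats missing items separately for Basic and Instrumental.

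Third, gaps should be uncommon. The scale is administered by a trained and certified rater (Protocol 8.3.1.7), assessments are monitored for quality (Protocol 8.3.1), and nothing in the documents suggests that missingness will differ by arm. This stands, and it limits the likely size.

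A reader might infer that incomplete forms are in general reported as functional decline. The rules do not support that. Only activities that would have been at maximum lose a point, matched gaps cancel, and Baseline gaps run the other way. A reader might also infer that a wholly blank form scores 0. The item rule contains nothing to prevent it, but SAP 9.1 uses observed cases and SAP 9.4.2 specifies observed data for this endpoint, so an assessment not done is more naturally read as giving no score.

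**Conclusion.** The concern holds in limited form. As written, SAP 5.4 records unanswered activities as dependence without limit, while the parent scores from the same form are withheld or prorated. The false change is at most 1 point per unanswered activity: a loss for a gap at Week 24 only, a gain for a gap at Baseline only. Bias in the treatment comparison needs missingness that differs by arm. Under the assumed 15% against 5% scenario it is about 0.21 of 23 points.

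It would be wrong to infer that the trial's efficacy conclusions are at risk. Independence appears only as a tertiary subscore in SAP 9.4.2. Protocol sections 4 and 10.4.3 and SAP Table 3 do not name it, the gatekeeping in SAP 7.5 covers only the primary and secondary endpoints, and the Total, Basic and Instrumental scores are reported beside it under stricter rules. This is a desirable correction, not an essential one. The sizes rest on assumed scores and missing rates.

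**What to change.** Replace the two zero-scoring sentences after Table 6 in SAP 5.4 with a rule at the level of the 23 activities:

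- An activity with any answered part below its maximum scores 0, because its status is then known.
- An activity counts as missing only if its status cannot be determined from the answered parts.
- With one missing activity, the score is the observed sum × 23/22.
- With two or more, the Independence score is set to missing.

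The unit must be explicit because Table 6 counts sub-parts (8a, 8b and 8c, for example) as separate questions. Copying the parent-score rule directly would mix the two units. It could prorate over an activity already known to be below maximum. It would also void the score for any single Basic gap: on the assumptions in step 5 of the working, about 7.0% of forms at a 1% rate and 15.4% at 2%. Zero-scoring may be kept as a labelled sensitivity analysis.

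The cost is SAP wording, some programming, and the loss of some incomplete forms for this subscore. The documents give no item-missing rate. At an assumed independent 1% per activity, the share of forms with two or more missing is 1 − 0.99^23 − 23×0.01×0.99^22 = 2.2%. At 2% it is 1 − 0.98^23 − 23×0.02×0.98^22 = 7.7%.

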### 5.5. Controlled Oral Word Association Test (COWAT)

The COWAT, which is subtest of the Multilingual Aphasia Examination (Benton, 1994), is a verbal fluency test that measures spontaneous production of words beginning with some designated letter. The COWAT uses the three-letter set (F, A, S) to assess phonemic fluency. Individuals are given 1 minute to name as many words as possible beginning with one of these three letters. The procedure is then repeated for the remaining two letters.

The COWAT takes approximately 5 to 10 minutes to administer.

The COWAT total score is calculated as the sum of the number of correct (acceptable) words, as follows:

- The number of correct (acceptable) words starting with the letter **F** PLUS The number the sum of correct (acceptable) words starting with the letter **A** PLUS The number the sum of correct (acceptable) words starting with the letter **S**.

If any one (or more) of the number of correct (acceptable) words is missing, the COWAT will be set to missing.

### 5.6. Neuropsychiatric Inventory (NPI)

The full NPI (Cummings 1994) is a 12-item behavior rating scale composed of a structured interview of the caregiver, which assess psychiatric disturbance. In this study, only Parts A, B, D & E of the NPI will be performed, which assess delusions, hallucinations, depression/dysphoria and anxiety, respectively. Both the frequency and the severity and caregiver distress of each behavior are determined. This scale will be administered by a rater who is trained for this study.

Scores are assigned to questions as demonstrated in Table 7. No imputation for missing values is performed; thus, if an item is missing, the corresponding domain is not calculated (ie, is set to missing).

**Table 7: Scores for NPI Individual Questions (Study RVT-101-2001)**

Category	Numeric values assigned
Frequency is rated as:	1=Occasionally - less than once per week 2=Often - about once per week 3=Frequently - several times per week but less than every day 4=Very frequently - daily or essentially continuously present
Severity is rated as:	1=Mild - produces little distress in the patient 2=Moderate - more disturbing to the patient but can be redirected by the caregiver 3=Severe - very disturbing to the patient and difficult to redirect
Caregiver Distress is rated as:	0=no distress 1=minimal 2=mild 3=moderate 4=moderately severe 5=very severe or extreme.

For each behavioral domain (Parts A, B, C and E), the total score for that domain is calculated as the frequency score times the severity score.

There are two sub-scores that will be analyzed from the NPI:

- The 2-item sub-score, which is the sum of the total scores for Parts A and B (delusions and hallucinations domains)
- The 2-item sub-score, which is the sum of the total scores for Parts D & E (depression and anxiety domains)
- The Distress Scores will be presented as shifts from baseline to each time point, where values are rated as ‘worsened’, ‘no change’, or ‘improved’ from baseline distress score.

### **5.7. North East Visual Hallucinations Inventory (NEVHI)**

The NEVHI is a semi-structured interview that assesses visual hallucinations in elderly patients with visual and/or cognitive impairments (Mosimann 2008). The NEVHI has 3 sections. It will take approximately 3 minutes for subjects without visual symptoms and up to 12 minutes for subjects with hallucinations. Subjects must have a score of  $\geq 1$  on Section 1 (Phenomenology) in order to have been assessed for Section 2 (Severity) and Section 3 (Distress).

If there are no hallucinations identified (and thus the Phenomenology section is scored as a 0), then both severity and distress scores will also be 0.

- Section 1: Phenomenology. Screens for the presence of visual hallucinations and assesses hallucination phenomenology. Scoring ranges from 0 (no hallucinations) through 6. The following are the 6 types of phenomenology that can be reported (it is possible that an individual subject may have up to all 6 of these). Within Section 1, the score can range from 0 (all ‘NO’ response) up to 6 (all ‘YES’ questions).
  - 1.1 - Complex visual hallucinations
  - 1.2 - Illusions
  - 1.3 - Feeling of presence
  - 1.4 - Passage of Shadow
  - 1.5 - Other visual symptoms
  - 1.6 - Simple hallucinations
- Section 2: Severity. Assesses the severity of hallucinations by rating temporal aspects (frequency and duration) of hallucinations.
- Section 3: Distress. Assesses emotion, cognition, and behavior associated with the most prominent recurrent visual hallucination during the month prior to the assessment.

Missing Phenomenology data will be handled as follows:

- A Phenomenology section MUST have a non-missing total score in order for severity and distress scores to be calculated.

- If the Phenomenology section is completely missing, then the entire scale (including both severity and distress scores) is set to missing for all phenomenology types.

**5.7.1. Section 2 Scoring (Severity of Hallucinations)**

Table 8 provides the scoring methodology for Section 2 (Severity) for the NEVHI. For each phenomenology identified in Section 1 (except for 1.5, Other visual symptoms), a frequency (never, less than once a week, 1-6 time a week, daily) will be assigned a score. Further, the duration (less than 5 minutes, 5 min to 2 hours, longer than 2 hours) will also be assigned a score.

**Table 8: Frequency and Duration Scoring for Section 2 (Severity) of the NEVHI (Study RVT-101-200)**

	Answers in Section 1*:					
	1.1 CVH	1.2 Illusion	1.3 Presence	1.4 Passage	1.5 Other	1.6 SVH
2.1 How often have you had hallucinations** in the last month? (Frequency)					Not Calculated for this Phenomenology	
0 Never						
1 Less than once a week						
2 1-6 times a week						
3 Daily						
2.2 How long do your hallucinations** usually last? (Duration)						
1 Less than 5 minutes						
2 5 min to 2 hours						
3 Longer than 2 hours						
2.3 (for patients with multiple phenomenology): what hallucination has the highest impact on you? (indicate with 1)						

\* Section 1.1 refers to Complex visual hallucinations (CVH), 1.2: Illusions, 1.3: Passage of shadow, 1.4: Feeling of Presence, 1.5: Other, 1.6: Simple hallucinations (SVH).

\*\* refers to simple/complex hallucination, feeling of presence, passage of shadow etc.

A Severity score is quantified for each hallucination experience as a product of its frequency and duration. The Severity score can range from 0 to 9, with 9 being the worst score.

- Severity score = frequency score x duration score

Missing frequency or duration values will be handled as follows:

- If the frequency is missing for a given phenomenology, the Severity Score for that phenomenology will be set to 0.
- If the duration is missing BUT the frequency is non-missing for a given phenomenology, the duration score should be set to “1” (less than 5 min).

The Severity score is only calculated for hallucinations (CVH, Illusion, Passage, Presence, SVH). Hence severity score is NOT calculated for Other Visual Symptoms (1.5 Other in Table 8).

Recurrent CVH are known to have the strongest impact on patients followed by recurrent Illusions (Urwyler 2014). Each **Severity score** is thus adjusted using a multiplication factor as shown in Table 9.

- Adjusted Severity Score for each Phenomenology = Severity Score (Table 8) x Multiplication factor (Table 9)

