**Table 9: Multiplication Factor for each Severity Score for Each Phenomenology (Study RVT-101-2001)**

	1.1 CVH	1.2 Illusion	1.3 Presence	1.4 Passage	1.6 SVH
Multiplication factor	4	3	1	1	1

The Total Severity Score is the sum of the 5 phenomenology Adjusted Total Severity scores (and thus the Total Severity Score ranges from 0 to 90, with higher scores indicating worse overall severity of hallucination phenomena).

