### 5.7.3. Analysis of NEVHI Outcomes

Data will be presented in two ways:

1. Number (%) of patients:
  - a. worsening from baseline
  - b. remaining unchanged from baseline
  - c. improving from baseline.

This would be performed for each score separately (Total Severity Score and Distress Score). Patients with NO hallucinations (a Phenomenology score of 0) at a given visit would have a score of 0 for Severity and for Distress at that visit.

2. Mean changes over time in the Section 1 Total Score, the Total Severity Score and Distress Score.

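### The NEVHI rule for missing frequency also scores hallucinations reported as present as zero severity, so an unknown rating enters the tertiary analyses as if none had occurred

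*SAP*

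**What the plan says.** SAP section 5.7.1 rates severity for the phenomenologies reported in Section 1: "For each phenomenology identified in Section 1 (except for 1.5, Other visual symptoms), a frequency" is scored from 0 ('Never') to 3 (daily), and a duration from 1 to 3. The product rule is "Severity score = frequency score x duration score". Each product is multiplied by its Table 9 weight: 4 for complex visual hallucinations, 3 for illusions, and 1 each for presence, passage and simple hallucinations. The weighted scores are then summed, and "the Total Severity Score ranges from 0 to 90, with higher scores indicating worse overall severity of hallucination phenomena".

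Two missing-data rules follow:
- Frequency: "If the frequency is missing for a given phenomenology, the Severity Score for that phenomenology will be set to 0".
- Duration: "If the duration is missing BUT the frequency is non-missing for a given phenomenology, the duration score should be set to" the shortest category, which scores 1.

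Zero already has a meaning on this scale. SAP section 5.7 says that when no hallucinations are identified, "then both severity and distress scores will also be 0". Section 5.7.3 repeats it visit by visit: "Patients with NO hallucinations (a Phenomenology score of 0) at a given visit would have a score of 0 for Severity and for Distress".

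The Total Severity Score is a tertiary endpoint in SAP section 9.4.2. Change from baseline is analysed by MMRM and Wilcoxon test, both described as using observed data. The worsened/unchanged/improved shift is analysed by a CMH row mean score test.

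**The concern.** A blank frequency can mean two things. If the phenomenology was answered NO in Section 1, there is nothing to rate and zero is right. If it was answered YES, the patient reported the phenomenon and its frequency is unknown. The rule treats both alike.

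The only check before scoring is in SAP section 5.7: Section 1 must have a non-missing total. A phenomenology answered YES with a blank frequency passes that check, so the zero enters the total and nothing marks it as imputed. No sensitivity analysis is specified for this rule.

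What is at stake is the validity of one tertiary endpoint. It has some scientific weight, because Protocol section 3.3 links the 70 mg dose rationale to the receptor implicated in visual hallucinations. The CMH shift test is especially exposed, since an artificial drop of any size can move a patient into another category.

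**Working it through.** **Inputs.** Frequency 0–3 and duration 1–3 (SAP Table 8); weights 4, 3, 1, 1, 1 (SAP Table 9); the missing-frequency rule (SAP 5.7.1).

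**The plan's own figure.** The maximum per phenomenology is 3 × 3 = 9. The maximum total is 9 × (4 + 3 + 1 + 1 + 1) = 9 × 10 = 90, which reproduces the stated range.

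**The rule applied to patients who answered YES.** Adjusted severity = frequency × duration × weight. CVH is complex visual hallucination and SVH is simple hallucination.

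| Case | True baseline → Week 24 | Scored baseline → Week 24 | Scored change | Category |
|---|---|---|---|---|
| 1. Stable CVH, 3 × 3 × 4; Week 24 frequency missing | 36 → 36 | 36 → 0 | −36 | improved |
| 2. Stable CVH (3 × 2 × 4 = 24) and illusion (2 × 2 × 3 = 12); illusion frequency missing at Week 24 | 36 → 36 | 36 → 24 | −12 | improved |
| 3. CVH worsens from 2 × 2 × 4 to 3 × 3 × 4; Week 24 frequency missing | 16 → 36 | 16 → 0 | −16 (true +20) | improved |
| 4. Stable CVH, 3 × 2 × 4; baseline frequency missing | 24 → 24 | 0 → 24 | +24 | worsened |
| 5. New CVH at Week 24 with frequency missing | 0 → unknown | 0 → 0 | 0 | unchanged |
| 6. Stable SVH (1 × 1 × 1) with Week 24 frequency missing; CVH worsens from 1 × 1 × 4 to 2 × 2 × 4 | 5 → 17 | 5 → 16 | +11 (true +12) | worsened |

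The direction of the error therefore depends on which visit lacks the frequency, whether the baseline score for that item was above zero, and what the other items do.

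**Size in a group mean.** The documents give no missing rate, so the rates here are assumptions. Among patients truly unchanged at 24, if a share *p* lack the Week 24 frequency, the artificial mean change is −24 × *p*:
- *p* = 2%: −0.48
- *p* = 5%: −1.2
- *p* = 10%: −2.4

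The bias in the difference between two such arms is −24 × (*p* active − *p* placebo). It is zero if the rates are equal. At 5% against 2% it is −24 × 0.03 = −0.72.

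**Comparison with the SAP's other rules.**
- CAF (section 5.8) is also frequency × duration. Severity is missing if either part is missing, and 0 only when the clinician judges fluctuation absent.
- NPI (section 5.6) is frequency × severity. The domain is missing if an item is missing.
- NEVHI Distress (section 5.7.2) is missing if more than one response is missing.

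NEVHI severity is the exception among these, and no reason is given.

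**The case against.** The rule has a legitimate use. A patient with some phenomenologies and not others leaves frequency blank for the absent ones, and zero is then the correct contribution to the sum. The sentence may have been written with only that case in mind. This stands: the rule needs a limit, and removing it would be wrong. The interview is also given by a trained rater, the endpoint is tertiary and outside the gated testing, and NPI Parts A and B cover hallucinations without imputation. These points limit the consequence, but they do not make the score correct.

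Three stronger readings are tempting, and the documents do not support them.
- A reader might infer that a zero frequency contradicts a YES in Section 1, so that a reported complex hallucination cannot score below 1 × 1 × 4 = 4. However, section 5.7.1 lists 'Never' among the frequency answers for identified phenomenologies, and it gives each severity score a range starting at 0. Question 2.1 covers the last month, and the SAP states no recall period for Section 1. YES followed by 'Never' is therefore a permitted combination. The fault is that a missing answer is treated as that answer.
- A reader might infer that the frequency and duration rules are inconsistent with each other. Duration has no zero category. Both rules assign the lowest category defined.
- A reader might infer that missing data always count as improvement, or that the rule favours the drug. Cases 4 to 6 show otherwise for the first, and without missing rates by arm nothing supports the second.

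**Conclusion.** The rule is wrong as written for phenomenologies answered YES in Section 1. It gives an unknown frequency the score for no hallucination and passes that score to the MMRM, Wilcoxon and CMH analyses as if observed.

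For one patient with one affected item, the artificial change can reach 36 of 90 points. That is the extreme case: complex hallucinations, daily, over 2 hours, stable, with the Week 24 frequency missing. For a weight-1 item the limit is 9 points. A false improvement needs a missing post-baseline frequency, a baseline score above zero for that item, and no larger worsening elsewhere.

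The net effect on the treatment comparison is unknown. It depends on missing rates by arm and visit, which the documents do not give, and it could be negligible if such blanks are rare or balanced. Primary and secondary conclusions are unaffected.

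**What to change.** Amend SAP section 5.7.1 before unblinding:
- Score 0 only when the phenomenology is NO in Section 1, or when its frequency is recorded as 'Never'.
- When Section 1 is YES and frequency is missing, set that item's severity and the visit's Total Severity Score to missing, as section 5.8 does for the CAF.
- Report by arm and visit how often this occurs.

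The text change is small. The cost is lost totals, including visits where only a weight-1 item (at most 9 of 90 points) lacks its frequency and everything else was rated. A missing baseline total also removes the patient from the change analyses, because SAP Table 2 schedules no earlier NEVHI. The number lost cannot be predicted from the documents.

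Imputing a frequency of 1 is not an adequate substitute. The stable patient at 36 would score 1 × 3 × 4 = 12, a false improvement of 24 points, and would still be classed as improved.
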